### 3.2.2 DEFINITION OF RESPONDER AND NON-RESPONDER FOR THE SECONDARY AND EXPLORATORY ENDPOINTS

Table 4: Definition of Responder and Non-responder for HSIL Regression Endpoint	
Responder	Non-Responder
Subject with no histologic evidence of vulvar HSIL AND Subject who did not receive any non-study related treatment for vulvar HSIL	Subject with histologic evidence of vulvar HSIL or vulvar carcinoma at evaluation OR Subject who received non-study related treatment for vulvar HSIL

Table 5: Definition of Responder and Non-responder for Viral Clearance Endpoint	
Responder	Non-Responder
Subject with no evidence of HPV-16 or HPV-18 in vulvar tissue at evaluation AND Subject who did not receive any non-study related treatment for vulvar HSIL	Subject with evidence of HPV-16 or HPV-18 in vulvar tissue at evaluation OR Subject who received non-study related treatment for vulvar HSIL

Table 6: Definition of Responder and Non-responder for Complete HSIL Regression Endpoint	
Responder	Non-Responder
Subject with no histologic evidence of vulvar HSIL, LSIL (VIN1), or condyloma AND Subject who did not receive any non-study related treatment for vulvar HSIL	Subject with histologic evidence of vulvar HSIL, LSIL (VIN1), or condyloma at evaluation OR Subject who received non-study related treatment for vulvar HSIL

Table 7: Definition of Responder and Non-responder for Disease Non-Progression Endpoint	
Responder	Non-Responder
Subject with no histologic evidence of a worsening vulvar condition to vulvar cancer at Week 48 relative to baseline  AND  Subject who did not receive any non-study related treatment for vulvar HSIL	Subject with histologic evidence of worsening of vulvar condition to vulvar cancer at Week 48 relative to baseline  OR  Subject who received non-study related treatment for vulvar HSIL

Table 8: Definition of Responder and Non-responder for HSIL Regression or Viral Clearance Endpoint	
Responder	Non-Responder
Subject with no histologic evidence of vulvar HSIL  OR  Subject with no evidence of HPV-16 or HPV-18 in vulvar tissue at evaluation  AND  Subject who did not receive any non-study related treatment for vulvar HSIL	Subject with histologic evidence of vulvar HSIL or vulvar carcinoma at evaluation  AND  Subject with evidence of HPV-16 or HPV-18 in vulvar tissue at evaluation  OR  Subject who received non-study related treatment for vulvar HSIL

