### 3.2.1 DEFINITION OF RESPONDER AND NON-RESPONDER FOR THE PRIMARY ENDPOINT

A treatment responder is defined as a subject with no histologic evidence of vulvar HSIL and no evidence of HPV-16 or HPV-18 in vulvar tissue at evaluation and who did not receive any non-study related treatment for vulvar HSIL. A treatment non-responder is a subject with histologic evidence of vulvar HSIL or vulvar carcinoma at evaluation, or a subject with evidence of HPV-16/18 at evaluation, or a subject who received non-study related treatment for vulvar HSIL. Any case of histologically confirmed progression to carcinoma according to the PAC is considered a non-responder.

Responder and non-responder definitions ([Table 3](#)) take into account both histopathologic regression of vulvar HSIL and virologic (HPV-16/18) clearance from tissue samples since HPV persistence is an important factor in the clinical progression of HSIL.

Table 3: Definition of Responder and Non-responder for the Primary Endpoint	
Responder	Non-Responder
Subject with no histologic evidence of vulvar HSIL AND Subject with no evidence of HPV-16 or HPV-18 in vulvar tissue at evaluation AND Subject who did not receive any non-study related treatment for vulvar HSIL	Subject with histologic evidence of vulvar HSIL or vulvar carcinoma at evaluation OR Subject with evidence of HPV-16 or HPV-18 in vulvar tissue at evaluation OR Subject who received non-study related treatment for vulvar HSIL

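### Tables 6 and 8 of section 3.2.2 do not reliably make vulvar carcinoma a non-response: Table 6 omits it from both columns, and Table 8 passes it when HPV-16/18 is undetectable

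*Protocol*

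**What the plan says.** Section 3.2.2 of the Version 5.0 protocol sets out responder rules for the secondary and exploratory endpoints in Tables 4 to 8.

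- **Table 6** serves secondary endpoint 4, whose objective is regression to normal tissue. The responder histology is "Subject with no histologic evidence of vulvar HSIL, LSIL (VIN1), or condyloma" and the non-responder histology is "Subject with histologic evidence of vulvar HSIL, LSIL (VIN1), or condyloma at evaluation".
- **Table 8**, titled "Definition of Responder and Non-responder for HSIL Regression or Viral Clearance Endpoint", serves secondary endpoint 8 and exploratory endpoint 9. Its responder column joins absence of HSIL by OR to "Subject with no evidence of HPV-16 or HPV-18 in vulvar tissue at evaluation", and then by AND to "Subject who did not receive any non-study related treatment for vulvar HSIL", with no brackets. Its non-responder column joins "Subject with histologic evidence of vulvar HSIL or vulvar carcinoma at evaluation" by AND to detection of HPV-16 or HPV-18, and then by OR to non-study treatment.
- **Table 4** (HSIL regression) does name carcinoma, but only in the non-responder column.

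The general rule, "Any case of histologically confirmed progression to carcinoma according to the PAC is considered a non-responder", is in section 3.2.1, headed "DEFINITION OF RESPONDER AND NON-RESPONDER FOR THE PRIMARY ENDPOINT". The synopsis version is likewise headed for the primary endpoint. Section 3.2.2 does not repeat it. Footnote 5 of the synopsis defines absence of HSIL as normal tissue, LSIL or condyloma. Its marker is on the primary endpoint, secondary endpoints 2 and 8 and exploratory endpoint 9, but not on secondary endpoint 4 or on the tables.

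**The concern.** Carcinoma is the worst histologic outcome in this trial, and the protocol treats it as failure for the primary endpoint. For two further endpoint definitions the tables do not carry that through. Table 6 could report a woman with carcinoma as a complete regression, or leave her unclassified with nothing said about whether she stays in the denominator. Table 8 would report a carcinoma with cleared virus as a success. The unbracketed Table 8 responder column adds an ambiguity about women given non-study treatment, which the protocol foresees: section 1.1.8 allows additional excision, ablation or medical therapy at the Investigator's judgment. With about 22 and 11 evaluable women planned per arm, a single classification is visible in the reported rate.

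**Working it through.** There is no figure in the plan to reproduce; the check is of the logic. Code each woman by six yes/no facts: H (HSIL), Ca (carcinoma), L (LSIL), K (condyloma), V (HPV-16/18 detected in tissue), T (non-study treatment for HSIL). This gives 2^6 = 64 profiles. They are logical cases, not equally likely patients.

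**Table 6.** Responder = no H, no L, no K, no T. Non-responder = H or L or K or T. The columns are exact complements, and Ca appears in neither. With H, L, K and T all absent, Ca and V are free: 2 × 2 = 4 responder profiles, of which 2 contain carcinoma (Ca alone; Ca with V). If footnote 5 is read in, the responder column gains 'no Ca'. Two responder profiles remain and the 2 carcinoma profiles fall in neither column, because the non-responder column has not changed.

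**Table 8.** Non-responder = ((H or Ca) and V) or T. The responder column has two possible bracketings, each with or without footnote 5:

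| Responder column read as | Footnote 5 | Responder column only (with Ca) | Both columns (with Ca) |
|---|---|---|---|
| (no H or no V) and no T | no | 20 (8) | 4 (4) |
| (no H or no V) and no T | yes | 20 (8) | 0 |
| no H or (no V and no T) | no | 20 (8) | 20 (12) |
| no H or (no V and no T) | yes | 20 (8) | 8 (0) |

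First row: T absent; 3 of the 4 combinations of H and V qualify; Ca, L and K are free, so 3 × 8 = 24 profiles. Four of them (Ca and V present, H absent, L and K free) also meet the non-responder column, leaving 20. The 8 carcinoma profiles are those with Ca present, V absent and T absent, with H, L and K free (2^3 = 8). They are the same 8 in every row: neither the bracketing nor the footnote removes them.

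In the last row, the 8 profiles in both columns are women with neither HSIL nor carcinoma who had non-study treatment.

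**Table 4**, read equally literally: responder = no H, no T; non-responder = H or Ca or T. Carcinoma without HSIL or treatment meets both columns (2^3 = 8 of 64). Footnote 5, where it applies, reduces this to 0.

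**Size.** Planned arms are 24 and 12, with 90% evaluable at Week 48 (sections 3 and 8.3): 24 × 0.9 = 21.6, about 22; 12 × 0.9 = 10.8, about 11. One woman is 1/22 = 4.5 points or 1/11 = 9.1 points.

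**Check of the proposed wording.** With carcinoma added to Table 6, and Table 8 set to responder = (no H or no V) and no Ca and no T with non-responder as its complement, all 64 profiles fall in exactly one column of each table and none with carcinoma is a responder.

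**The case against.** Four points can be made for the text.

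1. Footnote 5 excludes carcinoma from absence of HSIL, and it is attached to endpoints 8 and 9. A reader might infer from the literal text that HPV-positive carcinoma without HSIL sits in both columns of Table 8. The documents do not support that as a firm finding: with the footnote and the bracketing '(no H or no V) and no T', the overlap is 0. The footnote does not rescue Table 6. Its marker is not on endpoint 4, and applying it anyway leaves the carcinoma case unclassified rather than a non-responder.
2. A reader might also infer that surgically treated women can be counted either way in endpoints 8 and 9. That needs AND to bind before OR, as in a programming language. The adjacent non-responder column makes non-study treatment sufficient for failure, and Tables 3 to 7 all use it as an overarching condition. The intended bracketing is fairly clear; what stands is that it should be written.
3. Carcinoma with cleared HPV-16/18 does meet the clearance part of a regression-or-clearance endpoint, and Table 5 scores her as a clearance responder. This is the best defence of Table 8. But Table 8 itself lists carcinoma among the failing histologies, and if success despite carcinoma is intended, the protocol does not say so. The cost of excluding her is real: the composite would no longer contain all of its virologic component.
4. The effect is limited. The primary endpoint has its own rule, carcinoma is captured by Table 7 and as an SAE, and the protocol describes progression as typically taking years. All of this stands, but none of it stops the same woman being listed as a success elsewhere.

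Surgery following the finding does not clearly settle the matter either. It comes after the evaluation sample, and the treatment condition concerns treatment for HSIL.

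**Conclusion.** The point holds as a wording fault in stated rules. Table 6 literally makes carcinoma without HSIL, LSIL or condyloma a complete-regression responder, and on the most favourable reading leaves her unclassified. Table 8 makes carcinoma with undetectable HPV-16/18 a responder on every reading tested. Both cases assume no non-study treatment for HSIL. The missing brackets are a lesser defect, with one bracketing clearly better supported.

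The endpoints concerned are secondary 4 and 8 and exploratory 9; the two secondary endpoints are reported as proportions with exact intervals and no p-values. The primary analysis is not touched. Cases are likely to be rare, and the document gives neither their expected number nor the number of women operated on before evaluation. The step of 4.5 or 9.1 points per woman assumes the planned arm sizes and 90% evaluability. Enrolment to the imiquimod arm was halted in Version 3.0, so its actual denominator may be smaller and the step larger.

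**What to change.** In section 3.2.2:

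- **Table 6:** add vulvar carcinoma to the non-responder histology and absence of carcinoma to the responder histology.
- **Table 4:** add absence of carcinoma to the responder column, so that the columns no longer overlap on a literal reading.
- **Table 8:** write responder = (no HSIL OR no HPV-16/18) AND no carcinoma AND no non-study treatment for HSIL; non-responder = every other evaluated woman.
- Repeat the carcinoma sentence of 3.2.1 in 3.2.2, for the histology-based endpoints and the Table 8 composite.
- State that Table 5 remains purely virologic, so a carcinoma case with HPV-16/18 cleared may be a responder there and a non-responder in Table 8.

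The cost is table wording and the matching derivation rules. No data collection, sample size, primary analysis or clinical procedure changes. The one consequence to accept openly is that Table 5 responders are no longer a strict subset of Table 8 responders.

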## 2.2 SECONDARY OBJECTIVES AND ASSOCIATED ENDPOINTS

Secondary Objectives	Associated Secondary Endpoints
1. Evaluate the safety and tolerability of VGX-3100 delivered IM followed by EP with CELLECTRA™ 2000, alone or in combination with imiquimod	1a. Local and systemic events for 7 days following each dose as noted in the Participant Diary. 1b. All adverse events including SAEs, AESI's, SUSARs, UADEs, and other unexpected AEs for the duration of the study (through Week 100 visit) 
2. Determine the efficacy of four doses of VGX-3100, alone or in combination with imiquimod, as measured by histologic regression of vulvar HSIL	2. Proportion of subjects with no evidence of vulvar HSIL  on histology (i.e. biopsies or excisional treatment) at Week 48 visit
3. Determine the efficacy of four doses of VGX-3100, alone or in combination with imiquimod, as measured by virologic clearance of HPV-16/18 in vulvar tissue	3. Proportion of subjects with no evidence of HPV-16/18  in vulvar tissue samples at Week 48 visit
4. Determine the efficacy of VGX-3100 , alone or in combination with imiquimod, as measured by histologic regression of vulvar HSIL to normal tissue	4. Proportion of subjects with no evidence of vulvar HSIL, no evidence of vulvar LSIL (VIN1), and no evidence of condyloma on histology (i.e. biopsies or excisional treatment) at the Week 48 visit
5. Determine the efficacy of four doses of VGX-3100 , alone or in combination with imiquimod, as measured by non-progression of vulvar HSIL to vulvar cancer as determined by histology	5. Proportion of subjects with no progression  of vulvar HSIL to vulvar cancer from baseline to Week 48 visit
6. Determine the efficacy of VGX-3100, alone or in combination with imiquimod, as measured by reduction in the surface area of the qualifying  vulvar lesion(s)	6. Percent reduction in the cumulative surface area of the acetowhite vulvar lesion(s) as determined by the quantitative analysis of standardized pre-biopsy photographic imaging of the qualifying lesion (s) at Week 48 compared to baseline  . Results will be classified as: no clinically significant lesion resolution (reduction in lesion size of 0-25%), partial lesion area resolution (>25% and <100% reduction), and complete lesion resolution (no visible lesion).

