In the event of worsening disease prior to the end of the study (i.e., Subgroup E), the subject will receive surgical treatment per the Investigator's judgment and will continue on study with vulvoscopy, but without further study treatment or biopsy. In the event of worsening disease at the final visit, the subject will receive standard of care treatment (not part of study activities) per their treating physician. If wide excision is conducted at or prior to the subjects last on site visit, the sample obtained will be sent to the PAC for evaluation. For a finding of carcinoma, subjects will receive surgical treatment, and be discontinued from study treatment. The event will be reported as an SAE per [section 7.1.4](#).

All visible lesions should be biopsied at Week 48. For subjects for whom Week 78 is their final visit, all visible lesions should be biopsied at Week 74. For subjects for whom the final visit is Week 96, all visible lesions should be biopsied at Week 96.

If there is a new lesion identified at evaluation, or a non-qualifying lesion that is rebiopsied and confirmed to be vulvar HSIL and HPV-16/18 positive at evaluation, a discussion will take place between the Medical Monitor and the Principal Investigator to determine if additional dosing at Week 52 is appropriate.

Pre-biopsy Vulvoscopy Finding	Minimally required procedure
No acetowhite lesion	Vulvar punch biopsy and lesion photography; biopsy should be conducted of the same qualifying lesion as study entry from the region of potentially most advanced disease based upon judgment of the Investigator; new lesions or lesions that did not qualify at baseline should be biopsied at evaluation.
Acetowhite Lesion	Vulvar punch biopsy and lesion photography; biopsy should be conducted of the same qualifying lesion as study entry from the region of potentially most advanced disease based upon judgment of the Investigator; new lesions or lesions that did not qualify at baseline should be biopsied at evaluation
Multiple acetowhite lesions	Vulvar punch biopsies and lesion photography; biopsy should be conducted of the same qualifying lesions as study entry from the region of potentially most advanced disease based upon judgment of the Investigator; new lesions or lesions that did not qualify at baseline should be biopsied at evaluation

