### 6.13 VULVOSCOPY, PHOTOGRAPHS, AND BIOPSIES

Eligible subjects are enrolled in the study based on the diagnosis of vulvar HSIL confirmed by the PAC. Subjects will undergo vulvoscopy to identify the lesion(s). Interval vulvoscopies will be performed at Day 0, Weeks 4, 12, 27, 48, 74, and at Week 96 for subjects completing Week 96 prior to or under Amendment 5.0. Vulvoscopic visualization of a normal appearing vulva is insufficient evidence to confirm disease regression. An additional visit may be scheduled to perform vulvoscopy if worsening of disease is suspected.

Digital photographs of the vulva will be captured after application of acetic acid to document the clinical findings. If a biopsy or surgical excision is performed, images of the vulva should be collected before and after the procedure. Each site will be instructed on 1) the technique for capturing the proper images using a standard approach, and 2) the process for uploading the images to a secure server.

In the case of multifocal disease, the two lesions that potentially contain the most advanced disease as judged by the Investigator and which is of adequate size to ensure that a visible lesion remains after punch biopsy should be chosen for vulvar biopsy and documented using photography.

Biopsies should not be performed at any visit other than at entry (screening), Week 48, Week 74, or at Week 96 for subjects completing these timepoints prior to or under Amendment 5.0, unless the PI suspects disease progression. All biopsy samples obtained prior to or at the final discharge visit must be sent to the PAC for review. Investigator guidelines for managing the findings of unscheduled biopsies for suspected disease progression are described in [Table 12](#). Consult the Medical Monitor for any planned departures from these guidelines.

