#### **7.1.4 EVENT REPORTING FOR DISEASE PROGRESSION OR EXCLUSIONARY HISTOLOGIC FINDINGS POST-STUDY TREATMENT**

After starting study treatment, if there is histologic confirmation of progression of HSIL to microinvasive or invasive squamous cell carcinoma, the event must be reported as an SAE. For the finding of carcinoma, subjects should be managed per routine standard of care (i.e. surgical excision), discontinued from study treatment but continue on study without further biopsy. Post-study treatment histologic diagnosis of carcinoma should also be reported as an SAE. In both instances the condition for SAE reporting should be categorized as a medically important event unless another criterion is met.

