#### **8.4 ANALYSES POPULATIONS**

Analysis populations will include:

- The modified intention to treat (mITT) population includes all subjects who receive at least one dose of Study Treatment and who have the analysis endpoint of interest. Subjects in this sample will be grouped to treatment arms as randomized. Analysis of the mITT population will be primary for the analysis of efficacy in this study.
- The per-protocol (PP) population comprises subjects who receive all doses of Study Treatments and have no protocol violations and who have the analysis endpoint of interest. Subjects in this sample will be grouped to treatment arms as randomized. Analyses on the PP population will be considered supportive of the corresponding mITT population for the analysis of efficacy. Subjects excluded from the PP population will be identified and documented prior to unblinding of the study database.
- The safety analysis set includes all subjects who receive at least one dose of Study Treatment. Subjects will be analyzed as to the treatment they received.

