## 8.9 EFFICACY ANALYSIS

The true treatment effect on the primary endpoint is  $p$ , where  $p$  denotes the true population probability of the primary endpoint for each arm. The primary hypothesis of superiority is:

$H_0: p \leq 0.02$  vs.  $H_1: p > 0.02$ , for each treatment study group separately.

A p-value for these hypothesis tests and corresponding 95% confidence intervals will be computed based on the exact method of Clopper-Pearson. Superiority will be concluded if the one-sided p-value is  $< 0.025$  and the corresponding lower bound of the 95% CI exceeds 0.02.

The secondary efficacy binary endpoints will be analyzed in the same manner as the primary hypothesis, but without the hypothesis test p-values. All of the efficacy binary endpoints will be analyzed in two ways: a) based on qualifying and new lesions, and b) based on all lesions. Also, the Week 74 binary endpoint will be analyzed overall, and according to four or five doses received, and the Week 96 binary endpoint will be analyzed overall, and according to four, five, or six doses received.

For the analyses, the efficacy time frame is defined by any time starting from 14 days prior to the -specified visit week.

The anatomic extent endpoint will be analyzed by calculating the mean percent change and associated 95% t-distribution based confidence interval. The percentage of subjects with no clinically significant lesion resolution (reduction in lesion size of 25% or less), partial lesion resolution (26-99% reduction), and complete reduction (100% reduction) will be summarized with point estimates and associated exact Clopper-Pearson 95% confidence intervals.

An exploratory analysis will examine clearance outside of the vulva. This will be analyzed in the same manner as vulvar clearance.

An exploratory analysis will examine the relationship between the primary efficacy endpoint and a) miRNA results, b) vulvoscopy results, and c) HPV results. Relationships will be examined with contingency tables and/or logistic regression models which model the primary endpoint versus these results and treatment group as regressor variables.

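### Table 7 and the 14-day efficacy time frame score non-progression at Week 48, although secondary endpoint 5 covers the whole interval from baseline, so a carcinoma found before Week 46 has no settled place in the result

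*Protocol*

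**What the plan says.** All references are to protocol version 5.0.

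- **Endpoint definition (section 2.2, endpoint 5; also the synopsis).** The endpoint is the proportion with no progression "of vulvar HSIL to vulvar cancer from baseline to Week 48 visit". This is an interval. The synopsis footnote defines progression as advancement to carcinoma on histology according to the Pathology Adjudication Committee (PAC), with no visit attached.
- **Scoring rule (section 3.2.2, Table 7).** There are two non-responder limbs, joined by OR. The first is "Subject with histologic evidence of worsening of vulvar condition to vulvar cancer at Week 48 relative to baseline". The second is "Subject who received non-study related treatment for vulvar HSIL". The responder column uses the same Week 48 reference for cancer.
- **Time frame (section 8.9).** For the analyses, "the efficacy time frame is defined by any time starting from 14 days prior to the -specified visit week". No endpoint is exempted.
- **Early biopsy (section 6.13).** Biopsies are confined to the scheduled visits "unless the PI suspects disease progression". Table 12 provides for a carcinoma result on such a biopsy.
- **After a carcinoma (sections 3.2 and 7.1.4).** "For a finding of carcinoma, subjects will receive surgical treatment, and be discontinued from study treatment". Such women are "discontinued from study treatment but continue on study without further biopsy".
- **Analysis set (section 8.4).** The mITT population is "all subjects who receive at least one dose of Study Treatment and who have the analysis endpoint of interest". Section 8.13 rules out imputation.
- **Carcinoma rule (section 3.2.1).** The statement that any PAC-confirmed progression to carcinoma is a non-response appears only under the primary endpoint. Section 3.2.2 does not repeat it.

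**The concern.** The endpoint and its scoring table describe different things. One asks whether cancer occurred at any time up to Week 48. The other asks whether cancer is seen at Week 48, in tissue that section 8.9 accepts only from Week 46 on. The two agree for a woman biopsied at Week 48. They part for a woman whose carcinoma was found earlier, because no biopsy follows that could supply Week 48 tissue.

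This is the only efficacy endpoint on progression to cancer. Under two of the available readings it can show 100% non-progression in an arm where a cancer was confirmed. The trial is open-label, so anyone choosing between the readings after such a case would know its effect on the result.

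**Working it through.** The protocol gives no expected figure for non-progression, so there is none to reproduce. The check applies the stated rules to one case.

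**1. Opening of the frame.** Week 48 is Day 48 × 7 = 336. The frame opens at 336 − 14 = Day 322, and 322 / 7 = Week 46. No closing bound is stated.

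**2. The test case.** Assume a PAC-confirmed carcinoma on an unscheduled biopsy at Week 20, followed by surgery and no further biopsy. Her only post-baseline tissue precedes Week 46.

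**3. Three ways to score her.**

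| Reading | Basis | Score |
|---|---|---|
| Missing | No tissue in the 8.9 frame, so no endpoint under 8.4; no imputation under 8.13 | Left out of mITT |
| Responder | No histologic evidence of cancer at Week 48 (Table 7, responder column), and surgery for carcinoma not counted as non-study treatment for HSIL | In numerator and denominator |
| Non-responder | Surgery counted under the treatment limb, or endpoint 5's interval wording overrides Table 7 | In denominator only |

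**4. Arm size.** Section 3 plans 24 and 12 women, and section 8.3 assumes 90% evaluable. 24 × 0.90 = 21.6, taken as 22; 12 × 0.90 = 10.8, taken as 11.

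**5. Effect on the reported percentage.** Section 8.9 specifies exact Clopper-Pearson intervals. When all n women are non-progressors, the lower 95% limit is 0.025^(1/n). Otherwise the limits are beta quantiles: B(0.025; x, n − x + 1) and B(0.975; x + 1, n − x).

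VGX-3100 alone, 22 women, one early carcinoma:
- missing: 21/21 = 100%; lower limit 0.025^(1/21) = 0.839, so 83.9 to 100;
- responder: 22/22 = 100%; lower limit 0.025^(1/22) = 0.846, so 84.6 to 100;
- non-responder: 21/22 = 95.5%; limits 77.2 to 99.9.

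With two early carcinomas in that arm, leaving them out gives 20/20 = 100% (83.2 to 100) and counting them gives 20/22 = 90.9% (70.8 to 98.9).

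Combination arm, 11 women, one early carcinoma: left out, 10/10 = 100% (69.2 to 100); counted, 10/11 = 90.9% (58.7 to 99.8).

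**6. Neighbouring tables.** Table 4 (HSIL regression) names carcinoma in its non-responder column. Table 6 (regression to normal tissue) lists HSIL, LSIL and condyloma but not carcinoma, so carcinoma alone does not literally make a woman a non-responder there.

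**The case against.** The strongest reply is that Table 7 should be read together with the endpoint it serves. Endpoint 5 says baseline to Week 48, and the footnote on progression has no visit limit. On that reading a woman with confirmed carcinoma at Week 20 has a known outcome. She has the endpoint of interest, nothing needs imputing, and she counts as progression. The treatment limb of Table 7 may also catch her: it needs no tissue and carries no Week 48 limit, and the investigational products in section 5.1 are VGX-3100 and imiquimod, so surgery could be regarded as non-study treatment.

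This reply stands in part. It shows that a reader might infer too much by concluding that every early carcinoma is necessarily lost from the endpoint. The documents do not support that; loss is one of three possible scorings. But the reply does not settle the matter. The treatment limb requires treatment that is both unrelated to the study and given for HSIL, whereas this surgery is directed by the protocol and given for carcinoma. Section 3.2 labels some care as outside study activities but does not so label the surgery for carcinoma. Nothing says that section 2.2 overrides Table 7, or that the 8.9 frame spares an interval endpoint.

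It is also tempting to say that 46 of 48 weeks, or 96% of the risk, goes uncounted. That figure is calendar time, not expected loss. Sections 1.1.3 and 1.1.8 describe progression as typically taking years (one cited series has a mean of 2.5 years, with a range starting at 4 months), entry requires PAC confirmation of HSIL and not carcinoma, and post-screening tissue before Week 48 is taken only on suspicion.

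Finally, no cancer goes unreported: section 7.1.4 requires an SAE report, and secondary endpoint 1b covers SAEs.

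**Conclusion.** The contradiction is real and stands in the current text. Endpoint 5 is cumulative; Table 7's cancer limb and the 8.9 frame are not, and no sentence reconciles them. A carcinoma confirmed before Week 46 can therefore be omitted, scored as a success or scored as progression. For one such case among 22 women, the report is 100% under the first two readings and 95.5% under the third, a difference of 4.5 percentage points. In the combination arm, omission against counting differs by 9.1 points for one case among 11.

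These sizes rest on an assumed number of early carcinomas, which the protocol does not give and which may be zero, and on the planned arm sizes at 90% evaluable. The endpoint is secondary and has no hypothesis test, so no confirmatory conclusion depends on it. The reason to act is that the endpoint meant to count cancers should have one rule, fixed before any case has to be classified.

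**What to change.** - **Table 7, both columns:** replace the Week 48 time reference with *at any time from first dose through the Week 48 evaluation*.
- **Section 8.9:** state that the 14-day time frame does not apply to non-progression. A woman with PAC-confirmed carcinoma in that interval counts as progression and stays in the mITT denominator whether or not Week 48 tissue exists.
- **Table 6:** add carcinoma to the non-responder column, as in Table 4.
- **Tables 5 and 8:** leave unchanged. Carrying the carcinoma rule into them would change what the viral clearance component measures.

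The cost is wording in sections 3.2.2 and 8.9. The PAC readings and SAE reports it relies on are already collected, and no visit, procedure or clinical decision changes. The one downside is that the reported non-progression percentage may become slightly less favourable.
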